11.2. Appendix 2: Time & Events

The following two tables have been copied from the protocol.

11.2.1. Time and Events Table

Procedures ^{1,2}	Screening ³	Randomization ³ /Baseline (can be same day as Screening Visit)	Study Drug Check Phone Call (4-6 wks post rand.)	Clinic Visit Month 4 ± 18 days then every 4 months ± 18 days throughout the study	Unscheduled dose adjustment visit (if warranted)	Final study clinic visit ⁴ (or early withdrawal)	Follow up Phone Call 5 ± 1 weeks after last IP dose
Written informed consent	X						
Review of Inc/excl criteria	X	X					
Demography & directed medical history	X						
Assessment of MACE and micro-vascular events				X		X	
HbA1c	X ⁵			X		X	
Serum creatinine (eGFR)	X ⁵			X (alternate visits) ²		X	
Liver Function Tests (LFTs) ⁶		X		X (alternate visits) ²		X	
Record available information on most recent lipid assessment ⁷		X		X (annually)		X	
Genetic sampling ⁸		X					
Patient reported outcomes questionnaires ⁹		X ¹⁰		X (alternate visits) ²		X	
Key concomitant non-diabetes medication		X		X		X	X
Diabetes medication		X		X		X	X
Study drug reminder			X	X	X		
Physical examination ¹¹		X		X (alternate visits) ²		X	
SAEs, AEs of special interest, AEs leading to IP discontinuation		X	X	X	X	X	X
Pregnancy test ¹²	X	X					
Study drug dispense/compliance ¹³		X		X	X	X	

1. Subjects who discontinue investigational product should be handled as described in Protocol Section 4.4 and Section 4.5. and Table 2 .
2. Assessments at month 8, 16, 24 etc. will include patient reported outcomes questionnaires, serum creatinine (eGFR), LFTs and physical examination. Those at months 4, 12, 20 etc do not.
3. Screening and Randomization can occur at the same visit if all eligibility information is available. If Screening and Randomization occur at the same visit assessments should not be duplicated.
4. Once it is projected that the target number of MACE events will have been collected, a 3 month window will be defined for conducting the final, face to face visit.

5. HbA1c and creatinine assessed using local laboratories at Screening visit and measured no more than 6 months prior to randomization. If HbA1c or creatinine have not been assessed in the previous 6 months assessments to be performed via a central laboratory and results available prior to randomization. The investigator has the discretion to repeat screening HbA1c, and/or creatinine, based on clinical rationale even if previously available local results meet the eligibility criteria to allow the investigator to accommodate the possibility of change between screening and randomization.
6. Liver function tests: ALT, AST, alkaline phosphatase, bilirubin, GGT. Blood samples for LFTs at randomization must be collected prior to the first dose of investigational product.
7. Lipid values (TC, LDLc, HDLc, Tg) to be recorded as available from routine clinical care at baseline and annually thereafter. If results are unavailable, lipids tests are not to be performed for the study.
8. Informed consent for genetic research must be obtained before collecting a sample. This can be collected at any time after genetic consent has been obtained and randomization has occurred.
9. TRIM-D, EQ-5D and study specific questionnaire (details in Protocol Section 6.3).
10. TRIM-D is not required for subjects whose diabetes is treated by diet and exercise alone at Baseline.
11. See Protocol Section 6.2.7.
12. Only applies to women of child bearing potential. At screening perform urine pregnancy test. If positive, send serum sample to the central laboratory for confirmation. At Randomization perform a urine pregnancy test. If result is positive do not randomise the subject. If the urine pregnancy test is negative then the subject can be randomized. If Screening and Randomization are to take place at the same visit then follow the instructions for Screening. See Protocol Section 6.2.6.
13. Study drug dispensing not performed at final visit, compliance check not performed at Randomization.

11.2.2. Time and Events Table for Subjects Who Permanently Discontinue IP Prior to the End of the Study

Procedures	Clinic visit as soon after permanent discontinuation of IP as possible	Phone Call 5 ± 1 week after last IP dose	Continue contact schedule established at randomization 4 monthly ± 1 month. Telephone ^{1,2}	Continue contact schedule established at randomization 4 monthly ± 1 month. Clinic visit ^{1,3}	Final study clinic visit ⁴
Assessment of MACE and micro-vascular events	X		X	X	X
HbA1c	X			X	X
Serum creatinine (eGFR)	X			X	X
Liver Function Tests (LFTs) ⁵	X			X	X
Record available information on most recent lipid assessment ⁶	X		X (annually)	X (annually)	X
Patient reported outcomes questionnaire ⁷	X				
Key concomitant non-diabetes medication	X	X	X	X	X
Diabetes medication	X	X	X	X	X
Physical examination ⁸	X			X	X
AEs leading to IP discontinuation	X				
SAEs, AEs of special interest,	X	X	X	X	X
Study drug compliance	X				

1. After subjects permanently discontinue IP, follow-up should continue on the 4-monthly schedule established at randomization.
2. Where a subject would have been scheduled to attend clinic at months 4, 12, 20, 28 etc after randomization, a telephone contact will be performed instead (with assessments as shown above).
3. Where a subject would have been scheduled to attend clinic at months 8, 16, 24, 32 etc after randomization, a clinic visit will be performed (with assessments as shown above).
If a subject who has permanently discontinued IP is unable to attend clinic then they will be contacted by telephone instead and the telephone contact assessments will be performed.
4. Once it is projected that the target number of MACE events will have been collected, a 3 month window will be defined for conducting the final, face to face visit.
5. Liver function tests: ALT, AST, alkaline phosphatase, bilirubin, GGT.
6. Lipid values (TC, LDLc, HDLc, Tg) to be recorded as available from routine clinical care annually. If results are unavailable, lipids tests are not to be performed for the study.
7. TRIM-D, EQ-5D and study specific questionnaire (details in Protocol Section 6.3).
8. See Protocol Section 6.2.7.

11.3. Appendix 3: Assessment Windows

11.3.1. Assessment Windows

Data will be analyzed based on the visit information recorded in the eCRF. Data for unscheduled visits (including AESI labs and vitals and also CV event vitals), final study clinic (i.e., End of Study) visits (those scheduled to occur within the 3 month window), follow-up phone calls (5 ± 1 weeks after last IP dose) and early withdrawal visits will be assigned to a scheduled visit if the visit date falls within the corresponding protocol-defined visit window (Section 11.2) as specified. For lab data other than lipids the assignment to post-baseline visits will only be done for Central lab data (local lab data will be excluded).

Scheduled Visit	Target Study Day of Visit	Slotting Intervals
Screening	Not applicable	Not applicable
Randomization/Baseline	1	Not applicable
Month X, X=4, 8, 12, 16, etc.	X calendar months after the randomization date. If there is no such date then target is the latest day of that month. For example, if randomization is 31 July then Month 4 target date is 30 November.	Target study day +/- 18 days (inclusive)

Lipid data from local labs are recorded in the Lipids Collection log eCRF. Baseline values will be determined as per Section 11.5.2. Post-baseline values will be assigned in the following manner:

Scheduled Visit	Target Study Day of Visit	Slotting Intervals
Month 12	Month 12 visit date	(treatment start date + 1) to Month 12 visit date (inclusive); if treatment start date is missing then use randomization date instead
Month 24.	Month 24 visit date	(Month 12 visit date + 1) to Month 24 visit date (inclusive)
Month 36, etc.	Analogous to Month 24	Analogous to Month 24

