
Statistical Analyses

 For severe hypoglycaemic events during the On-therapy time period an additional recurrent event analysis will be performed in a manner similar to that done for MACE (see Section 7.1.2). As a sensitivity analysis, this will also be done for the On-treatment time period. It is recognized that sulfonylurea /insulin use may increase risk of hypoglycaemic events; hence the recurrent events analysis will be also be done stratified by baseline sulfonylurea/insulin use (yes, no). Summaries and analyses of eGFR will be based on values from scheduled visits computed using the protocol-specified formula based on the measured creatinine, including baseline local and Central lab creatinine data and post-baseline scheduled visit Central lab creatinine data. For change from baseline eGFR, treatment group comparisons will be done using a MMRM analysis as previously described using an On-treatment analysis. Due to the event-driven nature of the study, beyond Month 16 only summary statistics will be provided. In addition, eGFR will be categorically summarized by visit as Normal ≥ 90, Mild ≥ 60 to < 90, Moderate ≥ 30 to < 60, and Severe < 30. Shift tables of eGFR from baseline to post-baseline planned relative timepoints will be provided including a summary of the shifts to the most severe eGFR category determined post-baseline. 
Sensitivity analyses will be done using the protocol-specified equation and measured creatinine, including baseline and post-baseline scheduled visit Central lab creatinine data. These will include the MMRM analysis and the shift tables.

Model Results Presentation

 For time to event endpoints, p-values and estimates of hazard ratios and 95% confidence intervals (CIs) will be presented, along with Kaplan-Meier (KM) curves by treatment group. For change from baseline endpoints, least square means, 95% CIs and nominal p-values will be presented, along with plots of least square means vs time by treatment group.

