11.6. Appendix 6: Derived and Transformed Data

11.6.1. General

Multiple Measurements at One Time Point

- If there are multiple valid records for an assessment within an assigned analysis visit (i.e., assigned by site and/or assigned by slotting), only one of these records will be used for summary statistics and analyses. The record to be used is determined using the following hierarchy (in decreasing order):
 - the record closest to the target visit day
 - the record with an original nominal visit that matches the analysis visit
 - the record earliest in time
 - if the above does not result in a unique record, then the maximum assessment value of the records identified will be used in the determination of summary statistics
- Regardless of the determination of the record to be used for summary statistics, if data are listed, all data will be presented.
- Subjects having both High and Low values for Normal Ranges at any post-baseline visits for safety parameters will be counted in both the High and Low categories of “Any visit post-baseline” row of related summary tables. This will also be applicable to relevant Potential Clinical Importance summary tables.

Randomization Date

- Date subject was randomized as recorded in the eCRF.

Treatment Start Date

- First IP start date

Study Completion/Withdrawal Date

- Date of subject completion or withdrawal is recorded in the eCRF and corresponds to the date of withdrawal for subjects withdrawing from study (date at which the investigator agreed, or determined, that the subject's participation in the study was over; typically, this will be last study visit date) or date of completion of study (last study visit date) for subjects who complete the study (per Section 11.7.1). Subjects who die while on study are considered to have completed the study and completion date is the date of death. For subjects lost to follow-up, the date of withdrawal corresponds to the last contact between the Investigator and the subject during the study period as defined in the protocol.

Treatment Stop Date

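### Event-triggered labs and vitals can displace the planned value in by-visit safety summaries, because closeness to the target date ranks above the nominal visit (minor)

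*SAP*

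**What the plan says.** **Slotting.** SAP Section 11.3.1 defines Month 4, 8, 12, 16... slots as "Target study day +/- 18 days (inclusive"). Records placed in these slots by date include "Data for unscheduled visits (including AESI labs and vitals and also CV event vitals"). Final-visit records, follow-up calls and withdrawals are treated the same way: "early withdrawal visits will be assigned to a scheduled visit if the visit date falls within the corresponding protocol-defined visit window". For laboratory tests other than lipids there is a filter: "the assignment to post-baseline visits will only be done for Central lab data (local lab data will be excluded"). Vitals have no such filter.

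**Choosing one record per slot.** Section 11.6.1 applies to records assigned by the site or by slotting, so planned and slotted records compete. The first criterion is "the record closest to the target visit day". The second, reached only on a tie, is "the record with an original nominal visit that matches the analysis visit".

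**What is planned when.** Note 2 to the Time and Events Table (Section 11.2.1) places creatinine, liver function tests and physical examination at Months 8, 16, 24 and so on. Of the visits in between it says: "Those at months 4, 12, 20 etc do not".

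**Restriction for renal measures.** Section 8.2.2 states: "Summaries and analyses of eGFR will be based on values from scheduled visits". Notes 22 and 25 to Table 7, and Section 9.2.1 for creatinine, likewise refer to post-baseline Central-lab data from scheduled visits. Blood pressure, heart rate and liver tests carry no equivalent wording.

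**The concern.** Whether an event-triggered measurement exists depends on how the subject is at that moment. If such a value is chosen over the planned one because its date is more convenient, the by-visit sample partly depends on outcome. A heart rate recorded at a cardiovascular event could stand as the subject's Month 8 value while the planned Month 8 reading is dropped from the summary.

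Change in eGFR, blood pressure and heart rate are secondary safety endpoints (Section 2.2). Section 8.2.2 gives no model for blood pressure or heart rate, so their by-visit summaries, plots and clinical-concern tables are the whole analysis. By-visit eGFR categories (Section 8.2.2) and counts of creatinine at 1.5 and 2 times baseline (Section 9.2.1) are threshold displays, which acute values affect directly.

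The slots at Months 4, 12 and 20 are open even for assessments not planned there. The plan limits weight to baseline and every 8 months (note to Table 2.66), but Tables 3.150, 3.156 and 3.163 and Figures 3.08–3.09, 3.11–3.16 and 3.19–3.20 carry no such limit.

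**Working it through.** The SAP gives no figure for this rule, so there is none to reproduce. The check traces the rule and then sizes it under stated assumptions.

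**1. When the planned record loses.** Let the planned record lie s days from target (1 ≤ s ≤ 18) and let the event-triggered record fall uniformly on the 37 days of the window (assumption). It is strictly closer on 2s − 1 of those days, so the chance of displacement is (2s − 1)/37:

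| Planned visit off target by | Chance the event record replaces it |
|---|---|
| 0 days | 0% |
| 3 days | 5/37 = 14% |
| 7 days | 13/37 = 35% |
| 10 days | 19/37 = 51% |
| 14 days | 27/37 = 73% |
| 18 days | 35/37 = 95% |

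If the planned date is also uniform over ±18 days, a tie has probability (1 + 18 × 4)/37² = 73/1369 = 5.3%. The event record is strictly closer with probability (1 − 0.053)/2 = 47%. Ties keep the planned record.

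**2. How much calendar time the windows cover.** With the SAP's month of 30.4375 days, coverage is 37/(4 × 30.4375) = 30% on the 4-month grid. It is 37/(8 × 30.4375) = 15% on the 8-month grid, where creatinine and liver tests are planned.

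**3. Effect on the eGFR model.** The MMRM uses Months 8 and 16 only (Section 8.1.2, carried into 8.2.2). Assume 6% of subjects have an event-triggered Central-lab creatinine per 8-month cycle, with eGFR 20–25 ml/min/1.73m² lower; neither figure is in the SAP.
- Share of planned values replaced: 0.06 × 0.152 × 0.473 = 0.43%.
- Shift in an arm mean: 0.0043 × 20 to 0.0043 × 25 = 0.09 to 0.11 ml/min/1.73m².
- The shift is linear in the rate: 3% gives 0.04–0.05 and 12% gives 0.17–0.22.
- Only the difference between arms biases the contrast. At 6% versus 5% it is 0.01 × 0.152 × 0.473 × 25 = 0.018 at most.

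**4. What fills Months 4, 12 and 20.** On the same assumption, each off-cycle window receives about 0.06 × 0.152 × 9400 = 86 event-triggered creatinines. Final visits also include creatinine, liver tests and physical examination and are slotted by the same rule. If their timing were uniform on the grid, up to 0.152 × 9400 ≈ 1,430 would fall in off-cycle windows taken together, mostly the later ones. Early-withdrawal visits add to these. So can the clinic visit after IP discontinuation (Section 11.2.2), if it is recorded as unscheduled.

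**5. The renal wording.** On one reading, a scheduled visit is the nominal planned visit, and event-triggered creatinine is excluded from the eGFR and creatinine summaries. On the other, a record that Section 11.3.1 has assigned to a scheduled visit now counts as scheduled-visit data. Nothing in Sections 8.2.2, 9.2.1 or 11.3.1 decides between them, and two programmers could build different datasets.

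**The case against.** The rule is pre-specified and blind to treatment, and choosing the record closest to target is a common convention. Several points limit its reach, and they stand:
- Displacement is conditional. A planned visit on target is never displaced, and the 47% assumes planned visits spread evenly over the whole window.
- The Central-lab filter removes locally run acute-care results, including a worsening-renal-function creatinine measured locally.
- The scheduled-visit wording may already exclude event-triggered creatinine and eGFR.
- The schedule for blood pressure and heart rate is inferred from the physical-examination entry, whose content is in a protocol section not shown.

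A reader might infer that event-triggered values alone make up the Month 4, 12 and 20 points, so that plotted eGFR would dip there by 20–25 ml/min/1.73m². The SAP does not support this. Final and early-withdrawal visits enter the same slots, and at later months final visits could well outnumber event-triggered records. The 20–25 unit deficit is itself an assumption. A reader might also infer that the between-arm eGFR comparison is materially biased; the arithmetic above shows a very small effect.

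None of this changes the ordering in Section 11.6.1, the absence of any filter on vitals, or the undefined status of slotted renal records. Excluding event-triggered values does drop some observed safety data from by-visit means, but they can be kept in the displays meant to show extremes.

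**Conclusion.** The point holds as a minor one. As written, the rules let an event-triggered vital sign or Central-lab result replace the planned value whenever it is strictly closer to target. They also open off-cycle slots that, for creatinine, liver tests and physical examination, can contain only off-schedule records. The scheduled-visit restriction on eGFR and creatinine needs reconciling with the slotting rule.

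The primary MACE analysis is untouched. The effect on the Month 8/16 eGFR model is probably very small, about 0.1 ml/min/1.73m² per arm mean under the assumed 6% rate and 20–25 unit deficit, and less between arms. The real exposure is by-visit blood-pressure, heart-rate and liver-test summaries, categories and plots. Its size there cannot be computed from the SAP, which gives no event-measurement rates.

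**What to change.** Before unblinding:
- **Section 11.6.1:** rank the nominal-visit match first and closeness to target second.
- **Section 11.3.1:** do not slot AESI-triggered labs and vitals or CV-event vitals into by-visit summaries. Keep them in the any-post-baseline, worst-value, clinical-concern and listing displays.
- **By-visit displays:** limit creatinine, eGFR, liver-test and vitals displays to visits at which the assessment is planned, after checking the vitals schedule in the protocol.
- **Definition:** define scheduled visit once, and apply it in the notes to Table 7, Section 8.2.2 and Section 9.2.1.

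Displacement of planned values by event-triggered records then falls to zero. The cost is a few sentences and a changed sort order. A few subjects whose only value in a window is event-triggered become missing at that visit.

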11.4. Appendix 4: Treatment States and Phases

11.4.1. Treatment States for MACE

Treatment State	Definition
Pre-treatment	Event Date < Study Treatment Start Date
On-treatment	If event date is on or after treatment start date & on or before treatment stop date. Study Treatment Start Date ≤ Event Date ≤ Study Treatment Stop Date
Post-treatment	If event date is after the treatment stop date Event Date > Study Treatment Stop Date
Pre-therapy	Event Date < Study Treatment Start Date
On-therapy (during treatment or up to 56 days post-treatment)	If event date is on or after treatment start date & within 56 days after treatment stop date. Study Treatment Start Date ≤ Event Date ≤ Study Treatment Stop Date+56 days
Post-therapy	If event date is after the treatment stop date+56 days. AE Start Date > Study Treatment Stop Date+56 days

11.4.2. Treatment States for AE data

Treatment State	Definition
Pre-therapy	AE Start Date < Study Treatment Start Date
On-therapy (during treatment or up to 56 days post-treatment)	If AE onset date is on or after treatment start date & within 56 days after treatment stop date. Study Treatment Start Date ≤ AE Start Date ≤ Study Treatment Stop Date+56 days
Post-therapy	If AE onset date is after the treatment stop date+56 days. AE Start Date > Study Treatment Stop Date+56 days

NOTES:

- If the study treatment stop date is missing then the AE will be considered to be On-therapy.

If only partial information is available for the onset date of an AE, or onset date is missing, then the AE will be included in the most conservative therapy period (On-therapy > Post-therapy > Pre-therapy) that is consistent with the therapy period definitions above and the available AE onset and resolution date information.

11.4.3. Treatment States for lab and vitals data

Treatment State	Definition
On-treatment	If assessment date is after treatment start date & on or before treatment stop date. Study Treatment Start Date < Assessment Date ≤ Study Treatment Stop Date

11.5. Appendix 5: Data Display Standards & Handling Conventions

11.5.1. Study Treatment & Sub-group Display Descriptors

Study Treatment Descriptions			
PPD IRT		Data Displays for Reporting	
Code	Description	Description	Order
1	Albiglutide	Albiglutide	2
2	Placebo	Placebo	1

11.5.2. Baseline and Screening Definition & Derivations

11.5.2.1. Baseline Definitions

The baseline value for an assessment is defined as the last non-missing value assessed on or before treatment start date. Generally the time of assessment is not collected; hence this definition assumes that assessments collected on the same day as treatment start were done prior to treatment start. For creatinine, eGFR and HbA1c, if both local and Central Lab results are available for a given date then the Central lab value will be used.

For medication use, baseline use is defined as recorded data for which the start date of the medication is on or before treatment start date and the end date is on or after the treatment start date or ongoing or missing.

For subjects not receiving any study treatment, who therefore have no study treatment start date, baseline values and baseline medication use will be determined based on date of randomization.

11.5.2.2. Derivations and Handling of Missing Baseline Data

Definition	Reporting Details
Change from Baseline	= Post-Baseline Visit Value – Baseline
% Change from Baseline	= $100 \times [(Post-Baseline Visit Value – Baseline) / Baseline]$

NOTES :

- Unless otherwise specified, the baseline definitions specified in Section 11.5.2 will be used for derivations for endpoints / parameters and indicated on summaries and listings.
- Unless otherwise stated, if baseline data is missing no derivation will be performed and will be set to missing.

